3.2.6.9. HANDLING OF MISSING COVARIATE DATA FOR PS ANALYSES

The amount of missing baseline covariate to be used in the PS analysis is expected to be very small. This includes the missing numerical rating scores for a very small number of investigational device patients (~10) that were enrolled based on VAS pain scores. Prior to PS analysis, missing baseline covariates will be imputed using a single imputation based on multiple linear regression for continuous baseline covariates and multiple logistic regression for missing dichotomous baseline covariates.

3.2.6.10. PLANS TO ASSESS SITE POOLABILITY

Since different institutions are enrolling patients into the investigational and control groups, it is not possible to evaluate between site differences in relative efficacy. Therefore, analyses will focus on evaluating site variability in percentages of subjects achieving Month 24 CCS.

A random effects meta-analysis approach (DerSimonian and Laird³²) will be used to evaluate whether there is more site variability that can be explained by within site sampling variability. Success rates will be transformed to stabilize variances to meet the normality assumptions inherent in this approach. Site specific transformed success rates are assumed to follow a normal distribution with mean μ and variance τ^2 . The magnitude of site-to-site variability in the transformed success rates will be quantified using the I^2 statistics (Higgins et al 2004³³). I^2 is the fraction of τ^2 that is due to effect size heterogeneity, as opposed to sampling variance. Higgins *et al* indicate that, “A naive categorization of values for I^2 would not be appropriate for all circumstances, although we would tentatively assign adjectives of low, moderate, and high to I^2 values of 25%, 50%, and 75%”.

Therefore, the key quantitative assessment of whether or not site-to-site variability in treatment effect is important will involve the comparison of the observed I^2 value to the above guidelines. In addition to I^2 , the statistical significance of the site-to-site variability will be determined using the Q statistic with degrees-of-freedom equal to the number of sites minus 1. Sites contributing less than 6 patients will be combined prior to these analyses. If significant site variability is observed, sites will be removed one-at-time to identify site(s) contributing significant treatment effect heterogeneity and the identified site subjected to additional analyses aimed at understanding the cause of this heterogeneity.

3.2.6.11. [REDACTED]

[REDACTED]

[REDACTED]

[REDACTED]

[REDACTED]

³² DerSimonian R and Laird NM. Meta-analysis in clinical trials. *Journal of Controlled Clinical Trials*, 1986; 7:177-188.

³³ Higgins JP, Thompson SG, Deeks JJ, and Altman DG. Measuring inconsistency in meta-analysis. *BMJ* 2003, 327(7417): 557-560.

A bar chart showing the distribution of 1000 random numbers between 0 and 1. The x-axis represents the value of the random numbers, and the y-axis represents the frequency of each value. The distribution is highly skewed, with most values clustered near 0 and a long tail extending towards 1. The bars are black and have thin white outlines. The x-axis is labeled with numerical values from 0.0 to 1.0 in increments of 0.2. The y-axis is labeled with the word 'Frequency' and has numerical values from 0 to 100 in increments of 20. The distribution is unimodal and right-skewed.

3.2.6.12.

Term	Percentage
GMOs	95
Organic	95
Natural	95
Artificial	95
Organic	95
Natural	95
Artificial	95
Organic	95
Natural	95
Artificial	95
Organic	95
Natural	95
Artificial	95

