3.2.6.3. STUDY DESIGN

The 188 control subjects from [REDACTED]
[REDACTED] will be used to form a valid control group for determining the safety and effectiveness of the Simplify Disc device. Effectiveness comparisons will be performed using sub

classification through propensity score (PS) quintiles (Rosenbaum and Rubin, 1983)¹⁷. This approach directly addresses potential selection bias inherent in non-randomized comparisons.

The PS model will be evaluated according to rigorous criteria (Imbens and Rubin 2015)¹⁸ using a published heuristic (Maislin and Rubin 2010)¹⁹. Applications of this heuristic have been recently published (e.g., Keenan, Maislin, et al 2014²⁰; Arnardottir, Lim, Keenan, Maislin et al 2014²¹; and Pak, Keenan, Jackson, Grandner, Maislin et al 2014²²). The heuristic is designed to identify 5 sub classes in which the groups to be compared share the same multivariate distribution of a comprehensive set of baseline variables. Within each sub class, subjects are therefore equally likely to have received the Simplify Disc or conventional ACDF. The propensity score is the observational study analogue of complete randomization in randomized experiments in the sense that its use is not intended to increase precision but only to eliminate systematic biases in treatment-control comparisons (Rubin 2008)²³. Moreover, the "propensity score technique allows the straightforward assessment [of] whether the treatment groups overlap enough regarding baseline covariates to allow for a sensible treatment comparison" (Yue 2007)²⁴.

The PS sub classes will be formed when the prospective enrollment is completed in the investigational group. The standard implementation of the PS sub classification including iterative 'trimming' of subjects from the extremes of the PS distributions for both the

17 Rosenbaum PR and Rubin DB. The central role of the propensity score in observational studies for causal effects. *Biometrika* 1983a, 70:41-55.

18 Imbens and Rubin D. *Causal Inference in the Social and Biomedical Sciences* Cambridge University Press 2015 (in press)

19 Maislin G and Rubin DB. Design of Non-Randomized Medical Device Trials Based on Sub-Classification Using Propensity Score Quintiles, Topic Contributed Session on Medical Devices. *Proceedings of the Joint Statistical Meetings* 2010, pg 2182-2196.

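### Site poolability is judged on unadjusted single-arm success percentages but labelled as variability in treatment effect; the label should change and a case-mix-adjusted version should be pre-specified alongside

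*Combined protocol and SAP*

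**What the plan says.** Section 3.2.6.10 (Plans to Assess Site Poolability) begins from the fact that Simplify and ACDF patients come from different institutions, so "it is not possible to evaluate between site differences in relative efficacy". It therefore states that "analyses will focus on evaluating site variability in percentages of subjects achieving Month 24 CCS".

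The method is a DerSimonian-Laird random-effects analysis of transformed site success rates; the transform is not named. I-squared is read against benchmarks of 25% (low), 50% (moderate) and 75% (high), and this reading is called the "key quantitative assessment of whether or not site-to-site variability in treatment effect is important". Significance comes from the "Q statistic with degrees-of-freedom equal to the number of sites minus 1". On small sites: "Sites contributing less than 6 patients will be combined prior to these analyses".

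If significant variability is found, sites are removed one at a time to identify those contributing heterogeneity, again described as heterogeneity of treatment effect, with "the identified site subjected to additional analyses aimed at understanding the cause of this heterogeneity". The section names no baseline covariate. Section 3.2.6.3 says a rich common set of baseline covariates was collected in both studies, and section 3.2.6.9 expects very few missing values.

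**The concern.** The section rules out one quantity and then gives its name to another. Without a comparator at the site, a success percentage reflects the device, the surgeon and the setting, and the prognosis of the patients enrolled. Sites are not randomized to patients any more than devices are, yet the propensity-score care taken over the device comparison has no counterpart here.

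Two errors can follow. A site with harder patients can be flagged as a source of treatment effect heterogeneity although the device does equally well there. A weak site with easier patients may look ordinary and never reach the follow-up step. What is at stake is the meaning of the poolability statement in the study report, not the primary result.

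**Working it through.** **The text.** The opening of section 3.2.6.10 and its later use of *treatment effect* cannot both stand. This needs no arithmetic.

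**Inputs from the documents.** Up to 18 sites and N=182 (3.2.1); 154 evaluable Simplify and 128 evaluable control subjects, control rate 0.700, difference 0.035 (3.2.6.4). The Simplify rate used is 0.700 + 0.035 = 0.735. The 75.0% in the text of 3.2.6.4 does not match that difference; this is a separate matter.

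**The plan's own figures.** Section 3.2.6.10 has none to reproduce. The sample size that supplies the inputs does reproduce:
- controls: 188 × 0.85 × 0.80 = 127.8, or 128;
- enrolled Simplify: 154 / 0.85 = 181.2, or 182;
- SE = √(0.70×0.30/128 + 0.735×0.265/154) = 0.0539; power = Φ((0.035 + 0.10)/0.0539 − 1.645) = Φ(0.86) = 80.5%, stated as 80%.

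**Test statistics** for site *i* with O successes among n patients:
- crude: Q = Σ (Oᵢ − nᵢp̂)² / [nᵢp̂(1−p̂)];
- adjusted: Q = Σ (Oᵢ − Eᵢ)² / Vᵢ, with Eᵢ the sum of the patients' fitted probabilities p̂ⱼ from a logistic model on baseline covariates and Vᵢ = Σ p̂ⱼ(1−p̂ⱼ);
- I² = max(0, (Q − df)/Q), df = 18 − 1 = 17.

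**Assumptions not in the documents:** the prognostic strength of the covariates (SD on the logit scale) and the share of covariate variance lying between sites. No site effect is simulated, so every rejection beyond the nominal rate is a false flag.

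| Prognostic SD | Between-site share | Crude Q rejects | Adjusted Q rejects |
|---|---|---|---|
| 0.4-0.8 | 2-5% | 4.4-5.1% | 3.6-5.2% |
| 0.6 | 10 / 20 / 30% | 6.0 / 8.4 / 11.7% | 3.5-4.5% |
| 0.8 | 10 / 20 / 30% | 7.2 / 11.6 / 17.0% | 3.5-4.5% |
| 1.0 | 10 / 20 / 30% | 9.6 / 16.3 / 23.8% | 3.5-4.5% |

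The first row uses 154 patients at 18 sites, one covariate and 2,000 runs per setting. The others use 18 sites of 9, three covariates and 3,000 runs. Monte Carlo SE at a 5% rate is √(0.05×0.95/3000) = 0.4 points, or 0.5 points with 2,000 runs. A repeat of the four corner settings (SD 0.6 and 1.0, share 10% and 30%) gave 6.5, 10.9, 8.9 and 24.5%.

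**I-squared.** Over the last three rows, crude I² exceeds 25% in 20-48% of trials, against 13-15% adjusted. Crude I² above 50%, the plan's moderate level, is uncommon: at most 2.4% of runs up to SD 0.8 and a 20% share (4.2% with a Freeman-Tukey transform).

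**Effect of the transform.** With Freeman-Tukey rates and no case-mix difference at all, the crude test already rejects in about 7% of trials. With a mild difference (site-rate SD about 4.5 points) it rejects in 11%. Only about 11 − 7 = 4 points of that are case mix.

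**Power to find one poor site.** With one site worse by 1.0 logit (SD 0.8, share 10-20%), the test rejects in 14-17% of trials crude and about 8-9% adjusted.

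**Precision at one site.** 154/18 = 8.6 evaluable patients; 1.96 × √(0.735×0.265/8.6) = 0.30, or ±30 points.

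**The case against.** The other side has a good deal. The section states openly what it analyses, so the reference to treatment effect may be loose wording only. It provides for follow-up analyses of cause, where case mix could be examined. Entry criteria are shared and narrow, so between-site spread may be small, and then the excess is negligible. Sections 3.2.6.11 and 3.2.6.12 are redacted, so a covariate analysis there cannot be excluded.

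Most of this limits the size and leaves the point standing. The follow-up analyses are unspecified, start only after a significant result, and concern only the identified site. The visible text of 3.2.6.10 refers to no adjustment elsewhere.

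Three stronger readings are tempting and are not supported.

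- *That site-specific relative efficacy can be recovered through the propensity-score subclasses.* Section 3.2.6.3 says "Within each sub class, subjects are therefore equally likely to have received the Simplify Disc or conventional ACDF". That describes balance between device groups within a subclass. It does not say that one site's patients within a subclass resemble the controls. With no site contributing both devices, a site's own effect cannot be separated from its device effect. Observed minus ACDF-expected success would repeat the mislabelling, with an interval of at least ±30 points per site.
- *That the primary result rests on this assessment.* Nothing in sections 3.2.6.6 or 3.2.6.8 depends on I-squared or Q. The one-at-a-time removal is diagnostic, and no site is excluded from the primary test because of it.
- *That adjustment would reveal a poor site.* It would rarely do so; the number of patients per site is the limit.

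**Conclusion.** The point holds in a limited form. The wording is inconsistent on the face of the text. The planned analysis also cannot distinguish site performance from case mix, although the baseline data to reduce that confusion are collected.

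The false-flag excess is about 1 to 2 percentage points at low between-site spread (5-6% against 4%) and about 20 points at the high end (about 25% against 4%). A figure as high as 70% can be produced only by assuming that between-site SD equals within-site SD, that is 1/(1+1) = 50% of covariate variance between sites, which is not a reasonable headline. All these sizes rest on assumed spread and prognostic strength, on about 9 patients per site, and on no true site effect.

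Adjusted site rates are still not treatment effects, and unmeasured case mix remains in them. This is a worthwhile correction to a supporting analysis, not a threat to the non-inferiority conclusion.

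**What to change.** 1. In section 3.2.6.10, replace *treatment effect* and *treatment effect heterogeneity* by *site variability in success rates* throughout.
2. Keep the crude analysis. Alongside it, pre-specify the same Q, I-squared and one-at-a-time removal on observed minus expected successes per site. Do this separately for Simplify and ACDF sites, which the section leaves unstated. Take the expected values from a logistic model on a short fixed list of baseline covariates already collected, for example baseline NDI, age and neck pain, with the list fixed before outcomes are seen.
3. Name the variance-stabilizing transform, since the choice alone moves the false-flag rate.
4. State in the plan that adjustment removes only measured case mix, that power to find a single poor site is low, and that neither version alters the primary test.
5. Do not present observed minus ACDF-expected success as relative efficacy at a site.

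The cost is a few lines of text, a little more analysis work and one more table. No new data or visits are needed, and the sample size does not change. The ACDF part assumes that the control data carry site identifiers, which the documents do not state.

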3.2.6.13. SECONDARY EFFECTIVENESS ENDPOINTS

Secondary endpoints include:

- Clinically significant improvement in one or more radicular symptoms or myelopathy at each post-operative time point compared to baseline for the investigational two-level Simplify Disc and the two-level ACDF control group. The data collected will reflect the number of patients who improved (numbers will be stratified to reflect clinical improvement), who remain unchanged, and who deteriorated at each study time point. These endpoints will be graded and defined as follows:
 - Pain questionnaires will be used to evaluate each of the following pain locations:
 - Neck pain
 - Arm pain
 - Left arm pain (investigational group only);
 - Right arm pain (investigational group only);

Success is predicated on maintenance or improvement in neck and arm pain status according to the following equation:

Preoperative Score - Postoperative Score > 0

(Score = pain intensity + pain duration).

- Motor status - A change of one or more grade levels in muscle strength will be regarded as clinically significant.
- Sensory status - Sensation will be graded as normal or abnormal (diminished or absent). Any changes from abnormal to normal or absent to diminished will be regarded as clinically significant improvement.³⁵
- Time to recovery (time to first 15-point NDI improvement).
- Disc height (FSU Height) at each post-operative time point compared to baseline (6 weeks). Both levels have to be a disc height success to claim success for overall disc height. Disc height success for each level is based on either the anterior or posterior measurements meet the following criterions:

Postoperative Height – 6 Week Postoperative Height $\geq -2\text{mm}$

- Adjacent level deterioration at 24 months compared to baseline for the Investigational group.
- Displacement or migration of the device for the Investigational group; only changes of $> 3\text{ mm}$ will be considered significant due to the margin of error in radiographic determination of displacement distances.
- Return to work status postoperative.
- Subject satisfaction and perceived effect at each applicable postoperative timepoint. Success for each satisfaction question (three) will be defined as either a “Definitely True” or “Mostly True” response. Success for the perceived effect will be defined as either a “Completely Recovered,” “Much Improved,” or “Slightly Improved” response.

³⁵ Hacker *et al.*, *supra* note 7.

- Health Survey (SF-36) at each applicable postoperative time point compared to baseline. Success will be expressed in terms of the PCS (physical component summary) and MCS (mental component summary) scores and will be defined as a maintenance or improvement in status postoperatively as compared to the preoperative condition. To be classified as a success for each component summary, the following criteria must be met:

$$\text{PCSPostop} - \text{PCSPreop} \geq 0$$

$$\text{MCSPostop} - \text{MCSPreop} \geq 0$$

- Dysphagia Handicap Index (DHI scale) at each applicable postoperative time point compared to baseline for the Investigational group.
- Facet deterioration at 24 months compared to baseline for the Investigational group.
- Adjacent Level Motion (Stability) will be compared at each applicable postoperative time point to baseline.
- Results at each applicable postoperative time point will also be categorized by the physician's perception of the subject's condition (excellent, good, fair, or poor).
- Gait assessment at each applicable time point compared to baseline. This will be based on Nurick's classification. Success will be defined as maintenance or improvement in the postoperative status as compared to the preoperative condition:

$$\text{Preoperative Score} - \text{Postoperative Score} \geq 0$$

3.2.6.14. OTHER OUTCOMES

Other outcomes to be measured include:

- Duration of hospitalization;
- Blood loss;
- Operative time (skin incision to skin closure);
- In vivo endplate thickness analysis will be completed on a consecutive series of the first 25 subject who complete the 24 month follow up visit.

Radiographs will be used to monitor the occurrence of some of the above adverse events, including subsidence of the device into the adjacent disc or other changes in the implant, and spinal instability. In addition, at each visit, after the subject has had an opportunity to spontaneously mention any problems, the investigator will elicit information concerning adverse events by asking standard questions. Adverse events considered unusual for the patient population (i.e., occurring with greater frequency than anticipated or with greater severity than anticipated), key to safety or efficacy, or device related will require detailed reporting on the appropriate case report form.

Subgroup Analyses

Primary and secondary effectiveness endpoints will be evaluated in subgroups defined by stratifying the primary effectiveness analysis set. Safety endpoints will be evaluated in subgroups defined by stratifying the safety analysis set. Subgroups to be evaluated will include, but not limited to:

Gender (Male vs. Female)

Age (Median cut point, ≥ 55 and < 65 years)

Height (Median cut-point)

Weight (Median cut-point)

BMI (Median cut-point)

Comorbidities

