3.2.6.4. SAMPLE SIZE ANALYSIS

The current study is designed to demonstrate non-inferiority using a non-inferiority margin equal to -10.0% at a 1-sided type 1 error rate of $\alpha=0.05$. Subclassification using propensity score (PS) quintiles will be used to minimize selection bias arising from the non-randomized device group comparison. Mantel-Haenszel stratified analyses accounting for PS subclass will utilized when testing the primary non-inferiority hypothesis. A total of 182 two-level investigational subjects will be enrolled and compared to two level ACDF control subjects. The pool of two level ACDF control subjects includes a sample size of N=188. The sample size analyses below demonstrate that these sample sizes are sufficient to test the primary non-inferiority hypothesis after accounting for loss-to-following and PS ‘trimming’ of controls during the observational design phase.

According to Table 28 contained in the [REDACTED] SSED, the overall success was achieved in [REDACTED] controls. Therefore, the control group Month 24 CCS probability was assumed to be 70%. The total control sample size reported in the SSED is N=188. Since selection into a PS sub class will be conducted without access to outcome data, it is assumed that 85% of the selected controls will have a complete Month 24 CCS endpoint. It is also assumed that up to 20% of the controls will be trimmed as part of the PS modeling process. Therefore, for purpose on initial sample size analysis, the control sample size is assumed to be $N = 188 * .85 * .80 = 128$.

It is noted that the 2-level [REDACTED] group experienced an [REDACTED] success rate. For the purpose of sample size analysis, it is assumed that the 2-level Simplify disc

group will have at least a small true superiority margin of 3.5%. That is, it was assumed that the true probability of Month 24 CCS for the investigational group is 75.0%. As noted above, the primary effectiveness hypothesis is non-inferiority with a non-inferiority margin of -0.10 to be tested using at one-sided $\alpha=0.05$. With these assumptions, 154 investigational device patients are required for 80% statistical power as determined using industry standard software (nQuery Advisor 7.0 module PTE0U-1).

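### In the visible text, height, weight and BMI are specified for subgroup analysis only as median splits, with no device-by-covariate interaction, although a continuous interaction would answer the question with less loss of information

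*Combined protocol and SAP*

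**What the plan says.** The subgroup plan is a short block at the end of section 3.2.6.14 (Other Outcomes). For effectiveness it states that "Primary and secondary effectiveness endpoints will be evaluated in subgroups defined by stratifying the primary effectiveness analysis set"; safety endpoints are handled the same way in the safety set. The list opens with "Subgroups to be evaluated will include, but not limited to" and then names these entries:

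- "Gender (Male vs. Female)"
- "Age (Median cut point, ≥ 55 and < 65 years)"
- "Height (Median cut-point)"
- "Weight (Median cut-point)"
- "BMI (Median cut-point)"
- comorbidities, with no further definition.

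No test of interaction between device and covariate, no continuous modelling of effect modification, and no joint treatment of height or weight with gender appears in the visible text. Sections 3.2.6.6 and 3.2.6.7 define only the pooled non-inferiority and superiority tests. Sections 3.2.6.11 and 3.2.6.12 are redacted.

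**The concern.** A subgroup section asks whether the device difference depends on a patient characteristic. That is a question about a contrast of differences, and two separate half-sample results do not answer it. Each half is also imprecise, so one half may miss the margin while the other meets it even when the device effect is the same in both.

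Cutting a continuous variable at its median also discards information on effect modification. The control pool is fixed at 188, so that information cannot be recovered by enrolling more controls. Section 3.2.6.10 states that between-site differences in relative efficacy cannot be evaluated, because different institutions supply the two groups. Section 3.2.6.14 is therefore the main visible place where consistency of the device difference can be examined.

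A further issue is overlap. A pooled median for height will tend to separate men from women, so the height and gender subgroups may partly present one contrast twice.

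**Working it through.** **Inputs.** Section 3.2.6.4 gives 128 control and 154 investigational evaluable subjects, a control rate of 0.700, an expected difference of 0.035, and a test "using a non-inferiority margin equal to -10.0% at a 1-sided type 1 error rate of" 0.05. The running text of that section also gives an investigational rate of 75.0%, which does not equal 0.700 + 0.035 = 0.735.

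**Reproducing the plan's figure.** The documents give no figure for the subgroup analyses, so I checked the primary power, using the unpooled normal approximation.

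- SE = sqrt(0.735 × 0.265/154 + 0.70 × 0.30/128) = sqrt(0.001265 + 0.001641) = 0.0539.
- Power = Φ(0.135/0.0539 − 1.645) = 80.5%, against 80% stated.
- With 0.75 the same formula gives 87.7%, so the stated power rests on 0.735, which I use below. The choice hardly matters here: with 0.75 the SE is sqrt(0.75 × 0.25/154 + 0.21/128) = 0.0535.

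**Precision of the halves.**

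- SE within a half = 0.0539 × √2 = 0.0762. The 90% interval is ±1.645 × 7.62 = ±12.5 points, wider than the 10-point margin.
- Non-inferiority power within one half, if the planned difference holds everywhere = Φ(0.135/0.0762 − 1.645) = 55%.
- SE of the contrast between halves = 2 × 0.0539 = 0.1078.
- Contrast detectable with 80% power at two-sided 5% = 0.1078 × (1.960 + 0.842) = 30 points.

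**Information kept by a median split.** For a linear effect, this is the squared correlation between the covariate and its above-median indicator.

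| Covariate distribution | Kept | Lost |
|---|---|---|
| Normal | 2/π = 64% | 36% |
| Uniform | 75% | 25% |
| Lognormal, σ = 0.2 | 62% | 38% |
| Lognormal, σ = 0.3 | 59% | 41% |

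In the normal case, 282 evaluable subjects analysed by split are worth about 282 × 0.637 = 180 analysed continuously.

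**Power for a change of 10 points per SD** (an assumed size; normal covariate; two-sided 5%).

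- Split: the halves differ by 0.10 × 2 × √(2/π) = 0.160, so z = 0.160/0.1078 = 1.48 and power = Φ(1.48 − 1.96) = 32%.
- Continuous: the SE of the interaction per SD is about the overall SE, so z = 0.10/0.0539 = 1.86 and power = Φ(1.86 − 1.96) = 46%.
- More generally, an interaction with 80% power as a linear term has Φ((1.960 + 0.842) × √(2/π) − 1.960) = 61% as a split.

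These standard errors ignore PS stratification and imputation, so they are approximate.

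**Overlap with gender.** The documents give no distributions of gender, height or weight, so the gaps here are assumptions. I took normal distributions within each sex, equal within-sex SDs, and 40% to 50% men.

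- Height, male-female gap 1.8 to 2.2 SD: the median split agrees with gender for 80% to 86% of subjects.
- Weight, gap 0.5 to 1.0 SD: agreement is 60% to 69%, where 50% is chance.

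**The case against.** The strongest case against the point is that these are supportive analyses listed under Other Outcomes. Study success in section 3.2.6.2 depends only on the primary test, and no decision rule or error rate is tied to a subgroup. Categorical displays are a common descriptive choice. The text also does not say that the halves will be read in isolation. All of this stands, and it limits the point to an inexpensive improvement.

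Some stronger readings are tempting, but the documents do not support them.

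- A reader might infer that the plan excludes any other analysis. The list is open-ended, two nearby statistical sections are redacted, and section 3.6.8 refers analysis to the SAP. What can be said is that the visible text specifies no other method; an open list does not pre-specify an interaction.
- A reader might count age as a fourth median split. Its entry combines a median cut with a band from 55 to under 65 years, so the half-sample figures do not clearly apply to it.
- A reader might infer that the height and weight subgroups simply repeat the gender subgroup. No document data show this. Under the assumed gaps, 14% to 20% of subjects are placed differently by height and 31% to 40% by weight. That is strong overlap for height and partial overlap for weight.
- A reader might take the one-third loss as general. It needs a roughly normal covariate and a linear effect, and a split can do better if the true effect is a step.

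It is also fair to say that 46% power is still low. The continuous term makes better use of the data, but it does not make this an adequately powered test. The power figures depend on the level used: at two-sided 10% they are about 43% and 58%.

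**Conclusion.** The point holds as a low-severity improvement. For height, weight and BMI the visible text specifies only median splits evaluated within strata, and it names no device-by-covariate interaction. The within-half results (SE 7.6 points) do not address effect modification, and the contrast that would (SE 10.8 points) is not specified. Relative to a continuous linear term, the split gives up about 36% of the information under normality and linearity. For a 10-point change per SD, that is 32% power instead of 46% at two-sided 5%.

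The age entry needs clarification whichever method is used. Overlap of the height split with gender is likely but assumed. Nothing here affects the validity of the primary non-inferiority test or the study success criterion.

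**What to change.** In section 3.2.6.14:

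1. For age, height, weight and BMI, add for the primary endpoint a device-by-covariate interaction with the covariate kept continuous, on the risk-difference scale and adjusted for PS subclass. Report the change in device difference per SD with a confidence interval and a linearity plot.
2. Include gender and its interaction with device in the height model, and in the weight model as a check.
3. Keep the cut-point subgroups as a descriptive display, and state that any statement about effect modification rests on the interaction estimates.
4. State the age categories exactly: whether the median cut and the 55 to under 65 band are two separate groupings, and which groups are compared.

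The cost is a few sentences and a small number of supportive models on data already collected. To match section 3.2.6.8, each model would be fitted in the 20 imputed data sets and the results combined. The downside is the linearity assumption, which the plot lets the reader judge. Restricting the models to the primary endpoint keeps the work small. The primary test does not change.
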